Patients with electrical and chemical burns will be excluded, as will those with serious inhalation injury requiring treatment to maintain oxygen saturation. Patients in overt shock (defined as serum lactate >2.5 , or hypotension and altered mental status), Pregnant patients, psychiatrically unstable patients will be excluded.

Patients with oropharyngeal defects and/or previously known diagnoses leading to high risk of aspiration, and/or precluding safe nasal-enteric access will be excluded. Patients with history of chronic nausea and/or vomiting, including those with a diagnosis of gastroparesis due to diabetes mellitus will be excluded.

Patients with a Baux score of over 100 (age + TBSA), patients with declared palliative intent on admission, and patients for whom clinicians have high level of clinical concern based on clinical judgement will also be excluded.

Qualitative Component:

Inclusion Criteria

Healthcare workers (physicians, nurses, nursing assistants) who are anticipated to or have provided care to eligible patients in the enteral resuscitation arm of the study.

[figure not shown]
Exclusion Criteria

Exclusion criteria include co-PIs and co-investigators in this study to avoid bias.

11. Intervention

Please see schematic below for Intervention workflow. Specific goal-directed resuscitation protocols for IV fluid resuscitation and Enteral-based resuscitation in **Appendix** including details regarding modifications to allocated interventions based on response, patient request and improving/worsening disease.

Intervention Workflow Overview

General Resuscitation Protocol for Intravenous and Enteral-based Resuscitation

Resuscitation Timeline	Fluid Protocol	Clinical Assessment	Laboratory Assessment*	Additional Interventions
Hour 1	See Appendices A and B	Measure and record vital signs every two hours or more frequently as needed. (Temperature, blood pressure, heart rate, respirations, oxygen saturation), urine output, physical signs of overt shock	CBC, BMP, Lactate, PT/PTT/INR (15 mL)	Additional interventions such as colloid or blood product transfusion, vasoactive agents, escharotomy/ faschiotomy, intubation as deemed necessary by clinical care team will be noted throughout this time period.
Hours 2-7				
Hour 8	Administer Lactated Ringer's (LR) or Oral Rehydration Solution + LR according to calculated Parkland formula**		CBC, BMP, Lactate (10 mL)	
Hours 9-15				

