55	20%	2.3	212

15. Recruitment

Patients will be screened by research study team members for eligibility in the Emergency Department at Kirtipur Hospital. All recruitment and screening will occur in the Emergency Department and inpatient setting on admission. No outside recruitment will occur. The study will aim to enroll over the winter season, as this is the timeframe with the highest incidence rate of burn injuries in Nepal.

Methods

16. Allocation

The patient treatment allocation sequence will be generated using the sealed envelope technique. The sealed envelopes for each sequentially numbered enrolled patient (e.g. Patient 1, Patient 2, Patient 3, etc) will contain a pre-assigned intervention arm that will be unknown to the research team prior to each patient's enrollment. Each sealed envelope will only be opened after patient enrollment is complete to reveal patient intervention arm allocation.

17. Blinding

This study is not blinded to the patients or providers.

18. Data Collection Methods

Intervention:

In order to ensure a contextually appropriate intervention and increase engagement, data collection tools have been adapted from the validated Joint Trauma System Burn Care Clinical Practice Guideline 12 (JTS Burn Care CPG 12) burn worksheet and resuscitation flowsheet with feedback from stakeholders at the Nepal Cleft and Burn Center. Please see attached documents (Resuscitation Flowchart and Documentation Chart) for the latest versions developed by the research and clinician team, to be further adapted for ease of use as needed.

Clinical data pertaining to the resuscitation interventions will be collected and documented by the bedside nurses and clinicians on the adapted Documentation Chart, with documentation of i) brief history and physical exam ii) two-hourly assessments of vitals, intake, output, and symptoms and iii) 8 hourly laboratory test results. This data will subsequently be transcribed into a secure electronic format by research assistants utilizing the RedCAP data collection system.

Post-resuscitation patient interview answers will be recorded on the RedCAP data collection system.

Qualitative Component:

Data collection tools include focus group interview guide which will serve to guide the semi-structured 1-hour discussions pre-enrollment, at 50% enrollment and after completion of enrollment with groups of doctors and nurses caring for the patients enrolled in the study. The

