We will perform descriptive and comparative statistics for both qualitative and quantitative implementation metrics. Qualitative analysis of the patient and focus group interviews will use a template analysis approach to code and organize data for cross-case analysis of patterns of challenges and facilitators for each component of the resuscitation bundle.

21. Data Monitoring

The research team will conduct weekly virtual meetings (increasing frequency of meetings as needed) to discuss progress and relevant issues. We will measure against our internal timelines of progress, including enrolling 10 patients per month after enrollment begins. [name], study PI, and [name], study co-I, along with trained research assistants will be present for day to day monitoring, questions and problem solving. [name], U.S.- based PI will monitor all data submitted to RedCap for issues or patient safety concerns. [name], study co-I

and Assistant Professor of Surgery at University of Washington, will serve as a mentor for supervision and guidance on conducting the study.

Additionally, a Data Monitoring and Safety Board will be developed to monitor patient adverse events (AE) and serious adverse events (SAE). This is described below in section 22.

22. Harms

All patient clinical Adverse Events (AE) and Serious Adverse Events (SAE) will be monitored by study PIs. Furthermore, solicited or spontaneously reported adverse events will be reported to the study PIs. These will be investigated internally, in addition to reporting to the DSMB. All SAE will be reported to the DSMB within 1 working day of occurrence. All other AE and solicited or reported AE will be provided to the DSMB by study PI or Research Coordinator on a weekly basis.

Definitions:

Adverse Events (AE): are defined as those characterized as temporary in nature, mild symptomatology and no risk of long-term impact on morbidity and mortality, i.e. nausea/vomiting

Serious Adverse Event (SAE): those with risk of long-term impact on morbidity and mortality such as aspiration events, kidney injury requiring renal replacement therapy, and death.

Patients who experience serious adverse events attributed as a consequence of participation in the study may have costs of additional care (such as ventilation needs, renal replacement therapy needs) covered by the study.

23. Auditing

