Appendix B: Resuscitation Protocol Flowsheets and Documentation Chart

Enhanced Adult Burn Fluid Resuscitation Protocol for Intravenous Fluid Only Resuscitation

Use for Adults ≥ 18 years, not for pediatric patients, electrical/chemical burn patients or patients with suspected inhalation injury

- Baseline fluid calculation per Parkland Formula ($4\text{cc} \times \% \text{ TBSA} \times \text{weight (kg)} = 24\text{-hour fluid volume}$)
- Vital signs including Heart Rate (HR), Blood Pressure (BP), O₂ saturation and Urine Output (UO) should be tracked every 1 to 2 hours, with fluid rate adjusted accordingly
- **Target Urine Output = 0.5 mL/kg/hr; HR < 120 bpm; Systolic BP >90 mmHg**
- If hypotensive with EITHER Intravenous or enteral-based resuscitation, give bolus of 10cc/kg IV fluids. Consider vasopressor or colloid augmentation.
- For all calculated hourly resuscitation volumes, please round to the nearest 10 (i.e., 74 =70ml, 76=80mL)

[figure not shown]

Adult Burn Fluid Resuscitation Protocol for Enteral-based Resuscitation

Use for Adults ≥ 18 years, not for pediatric patients, electrical/chemical burn patients or patients with suspected inhalation injury

- Vital signs including Heart Rate (HR), Blood Pressure (BP), O₂ saturation and Urine Output (UO) should be tracked every 1 to 2 hours, with fluid rate adjusted accordingly
- Goal: UO=0.5 mL/kg/hr, HR < 120, Systolic BP >90
- If hypotensive with EITHER resuscitation type, give bolus of 10cc/kg IV fluids. Consider vasopressor or colloid augmentation.
- ORS can be administered by drinking or administering the calculated volume via NGT every hour
- For all calculated hourly resuscitation volumes, please round to the nearest 10 (ie 76=80mL)

Abbreviations: IV= Intravenous, RL= Ringer's Lactate, ORS= Oral Rehydration Solution, NGT= Nasogastric Tube

Today's Date: / / 2021			Date and Time of Injury: / / 2021; : AM/PM			InPatient No:							
Name		Admission Wt. (kg)	%TBSA (Do not include superficial 1 st degree burn)			Burn Mechanism							
Parkland Formula: Total Resuscitation Volume: _____ % X _____ kg X 4ml = _____ in 24 hours (TBSA) (pt. weight)						First 8 hours (use 1/2 of total volume) _____ ÷ 8 hrs. Starting Hourly Fluids = _____ ml/hour			Starting 2 Hourly I.V Fluid _____ ml				

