Target Urine Output: _____ kg x 0.5 ml/kg/hr = _____ per hour						Upper CutOff = _____ kg x 0.8 ml/kg/hr = _____ per hr Lower CutOff = _____ kg x 0.2 ml/kg/hr = _____ per hr			2 Hourly Urine Upper Cutoff: _____ ml Target: _____ ml Lower CutOff: _____ ml				
Resuscitation Start time: _____ : _____ AM / PM						Time post Incident: _____ Hrs _____ Mins							
Resus. Hour	Planned total fluid rate	AMOUNT OF FLUIDS GIVEN			Total fluids given (since last check)	Urine Output (q 2hrs)	VITALS		SYMPTOMS: ✓ if yes			Comments on symptoms or issues	CALCULATED RESUSCITATION FOR NEXT 2 HRS.
		Oral fluids		IV fluids			Additional fluids	Heart Rate	Blood Pressure	Oxygen Sat (%)	Nausea		
1 - 2						mL							
3 - 4						mL							
5 - 6						mL							
7 - 8						mL							
9 - 10						mL							
11 - 12						mL							

← Lower Cutoff

TARGET URINE OUTPUT

Upper Cutoff →

↑↑ Fluid by 20%

↑ Fluid by 10%

(continue same)

↓ Fluid by 10%

↓↓ Fluid by 20%

Resus. Hour	Planned total fluid rate	AMOUNT OF FLUIDS GIVEN			Total fluids given (since last check)	Urine Output (q 2hrs)	VITALS			SYMPTOMS: ✓ if yes				Comments on symptoms or issues	CALCULATED RESUSCITATION RATE FOR NEXT 2 HRS.			
		Oral fluids		IV fluids	Additional fluids		Heart Rate	Blood Pressure	Oxygen Sat (%)	Nausea	Vomiting	Distention	Reflux					
		By mouth	By NG															
13 - 14						ml												
15 - 16						ml												
17 - 18						ml												
19 - 20						ml												
21 - 22						ml												
23 - 24						ml												

Resuscitation Laboratory Results

Time of Resuscitation	CBC	BMP	Arterial Blood Gas	Coagulation Markers (PT/PTT/INR)
Admission	WBC: Hgb: Hct: Plt:	Na: K: BUN: Creat:	Lactate: Cl: HCO ₃ :	PT: PTT: INR:
Hour 8	WBC: Hgb: Hct: Plt:	Na: K: BUN: Creat:		
Hour 16	WBC: Hgb: Hct: Plt:	Na: K: BUN: Creat:		
Hour 24	WBC: Hgb: Hct: Plt:	Na: K: BUN: Creat:	Lactate: Cl: HCO ₃ :	PT: PTT: INR:
Hour 32	WBC: Hgb: Hct: Plt:	Na: K: BUN: Creat:		
Hour 40	WBC: Hgb: Hct: Plt:	Na: K: BUN: Creat:		
Hour 48	WBC: Hgb: Hct: Plt:	Na: K: BUN: Creat:	Lactate: Cl: HCO ₃ :	PT: PTT: INR:

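### The two-hourly bedside chart has no column for three of the seven clinical items Section 11 requires, and no structured field for intubation, vasoactive agents or aspiration, so the assessment-completeness endpoints have no fixed denominator

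*Combined protocol and SAP*

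**What the plan says.** Section 11, General Resuscitation Protocol table, clinical assessment column: "Measure and record vital signs every two hours or more frequently as needed", followed by the list "Temperature, blood pressure, heart rate, respirations, oxygen saturation), urine output, physical signs of overt shock". The last column of the same table names colloid or blood products, vasoactive agents, escharotomy or fasciotomy, and intubation, and ends "intubation as deemed necessary by clinical care team will be noted throughout this time period".

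Section 18 says that bedside nurses and clinicians fill in the Documentation Chart, which covers "two-hourly assessments of vitals, intake, output, and symptoms" along with a history and examination and the laboratory results. Research assistants then transcribe it into REDCap. The attached version is the latest but is "to be further adapted for ease of use as needed".

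Appendix B, Documentation Chart: the two-hourly grid has columns for planned and given fluids, urine output, heart rate, blood pressure and oxygen saturation. It has ticks for nausea, vomiting, distention and reflux, and one free-text column, "Comments on symptoms or issues".

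Section 12, under Primary endpoints, lists among its adherence measures the share of protocol laboratory and clinical assessments that were done and how complete the bedside documentation is. Hypothesis 1 expects adherence of at least 50%.

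Section 22 defines serious adverse events as "those with risk of long-term impact on morbidity and mortality such as aspiration events, kidney injury requiring renal replacement therapy, and death". Section 17 says neither patients nor providers are blinded.

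**The concern.** The chart is where the data begin. REDCap checks for required entries (Section 19) cannot recover a value that the paper form never asked for. Two things are at stake.

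The first is measurement of endpoints listed as primary. If completeness is scored against the chart, a patient can reach 100% with no temperature, respirations or shock signs ever recorded, and non-adherence to Section 11 is hidden. If it is scored against Section 11, missing data are built in by the form and will look like poor staff adherence. The plan does not say which standard applies.

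The second is safety data. Aspiration is a named serious adverse event and plausibly tied to the enteral route. Without a field that must be answered at every check in both arms, its recording depends partly on whether someone who knows the allocation thinks to write or report it. Capture could then differ by arm, in either direction.

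**Working it through.** The plan states no figure on this point, so there is none to reproduce. The check sets the Section 11 list against the Appendix B grid.

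**Clinical items (Section 11) and chart columns (Appendix B)**

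| Item | Column in two-hourly grid |
|---|---|
| Blood pressure | yes |
| Heart rate | yes |
| Oxygen saturation | yes |
| Urine output | yes |
| Temperature | no |
| Respirations | no |
| Signs of overt shock | no |

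Four of 7 are present and 3 of 7 (43%) are absent.

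**Events and interventions**

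| Item | Named in | Structured field |
|---|---|---|
| Intubation | Section 11 | no |
| Vasoactive agents | Section 11 | no |
| Escharotomy or fasciotomy | Section 11 | no |
| Colloid or blood products | Section 11 | at most the additional-fluids column |
| Aspiration | Section 22 | no (reflux is the nearest tick) |

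**Effect on a completeness score.** Inputs: 12 printed two-hourly rows (hours 1-2 to 23-24), 7 required items, 4 columns. Assumptions, since the plan gives no scoring rule: each item at each check counts equally, laboratory items are left out, and items without a column are not written in the comments.

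- Section 11 denominator: 7 × 12 = 84.
- Chart denominator: 4 × 12 = 48.
- Item-checks with no column: 3 × 12 = 36.
- A perfectly filled grid scores 48/48 = 100% against the chart and 48/84 = 57% against Section 11.
- To reach 50% against Section 11, 0.50 × 84 = 42 item-checks are needed, so 42/48 = 87.5% of the printed cells must be filled. Against the chart, 24 of 48 would do.

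**Narrower reading.** If the duty to record attaches only to the five vital signs in the bracket, 3 of 5 have a column. A perfect grid scores 36/60 = 60%, and 50% needs 30/36 = 83% of the printed cells.

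If staff write every missing item in the comments, the Section 11 score can rise to 100%. The score therefore depends on unprompted free text as well as on adherence. The same form serves both arms, so the ceiling is common to both. Hypothesis 1, however, is an absolute threshold, and there the choice of denominator matters.

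**The case against.** The strongest reply is that the chart is one form, not the whole data system. Section 22 has the PIs monitor all adverse events, receive solicited and spontaneous reports, and pass serious events to the DSMB within one working day. Section 21 adds PI review of REDCap data and research assistants on site. Section 13 follows patients for the hospital stay. The REDCap form is not in the documents and may have event fields. This stands. A reader might infer that aspiration is found solely through free text from unblinded staff, and the documents do not support that. What they lack is an aspiration definition, a schedule for soliciting events, and blinded adjudication.

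A reader might also infer that a planned between-arm comparison of aspiration is compromised. None is planned: Section 12 lists no aspiration endpoint and Section 20 names no such analysis. The issue is the quality of safety data.

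It is tempting to say Appendix B tells staff to skip temperature and respirations. Its wording is "Vital signs including Heart Rate (HR), Blood Pressure (BP), O₂ saturation and Urine Output (UO) should be tracked every 1 to 2 hours", and a list introduced by *including* is not exhaustive. It fails to prompt for those items but does not countermand Section 11.

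The laboratory rows show no glucose field, and a reader might infer that sugar in the ORS could distort urine output unseen. The documents neither say that the metabolic panel includes glucose nor describe such an effect, so that is not part of this point.

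Finally, the chart as read may be incomplete. In the text read from the PDF the hours 1-12 header breaks off after nausea, some figures are missing, and the history and examination part that Section 18 mentions is not visible. The hours 13-24 header appears complete and shows the same gaps, so the missing grid columns are unlikely to be a reading fault. A field for interventions elsewhere on the form cannot be ruled out. Section 18's allowance for adapting the chart permits the correction but does not make it.

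**Conclusion.** The mismatch is real and modest. As printed, the two-hourly grid has no column for 3 of the 7 clinical items that Section 11 requires, and no structured field for intubation, vasoactive agents or aspiration. The firmest consequence is for the two completeness measures under Primary endpoints: the same fully completed chart scores 100% or 57% (60% on the narrower reading), depending on a standard the plan does not name. Those figures assume equal weights, a 24-hour grid, and nothing added in free text.

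The aspiration consequence is weaker. Other reporting routes exist, so the conclusion is that capture may differ by arm. The documents do not show that it will, and no estimate of the size is possible from them.

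The conclusion rests on the extracted hours 13-24 header being complete, and on the REDCap form adding no bedside prompts of its own. This is an inexpensive improvement to the data, not a flaw that undermines the trial.

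**What to change.** 1. Add temperature, respirations and shock-sign columns to the two-hourly grid so that it matches Section 11.
2. Add yes/no fields with time for each additional intervention that Section 11 says will be noted: colloid or blood products, vasoactive agents, escharotomy or fasciotomy, and intubation.
3. Add an aspiration yes/no field, answered at every check in both arms. Put one written definition, applied identically in both arms, in Section 22.
4. State in Section 12 or 20 that the two completeness measures are scored against the Section 11 list.
5. Mirror the new fields in REDCap.

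The cost is a denser chart and a small REDCap edit. The clinical observations are already required, so no new bedside measurement is needed beyond answering the aspiration question. The aspiration field will still be completed by unblinded staff. It makes the prompt equal in both arms and the definition narrows room for judgement, but neither removes the effect of knowing the allocation.

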Hour 16	Add or subtract fluid volume by every 2 hours based on urine output goal of at least 0.5 mL/kg/hr.		CBC, BMP, Lactate (10 mL)	
Hours 16+	IV Metoclopramide to be administered if GI symptoms such as bloating, nausea, discomfort, vomiting.		CBC, BMP, Lactate every 8 hours, and PT/PTT/INR every 24 hours until resuscitation complete.	

* CBC=Complete blood count; BMP=Basic metabolic panel; PT=Prothrombin time; PTT=Partial Thromboplastin time; INR=international normalized ratio

**Parkland formula= $4\text{cc} * \% \text{ Total Body Surface Area burned(TBSA)} * \text{weight(kg)} = 24 \text{ hour fluid volume}$
Total resuscitation volume divided by 2, then divided by 8 to determine the starting resuscitation volume.

12. Outcomes

Goals

The overarching goals are to understand challenges and facilitators of enteral-based resuscitation and understand the effectiveness of the technique compared to standard of care (intravenous resuscitation).

Specific Aim 1: Determine the frequency of adherence to the enteral-based and IV fluid resuscitation protocols, and determine frequency of successful resuscitation.

Hypothesis 1: With goal-directed resuscitation, the primary outcomes of goal average urine output and successful resuscitation will be achieved in the majority of patients (over 50%). Protocol adherence will be at least 50%.

Specific Aim 2: Describe the challenges and facilitators to enteral and IV resuscitation protocol acceptance, implementation, compliance and sustainability.

Hypothesis 2: Enteral resuscitation will have logistical advantages over IV resuscitation, reduce delays in the initiation of resuscitation, have fewer interruptions, and will be easier to implement.

Primary endpoints

For the quantitative aspect, study variables will include measures of implementation and adherence to the enteral resuscitation protocol with variables such as: percent of resuscitation conducted enterally, proportion of protocol laboratory and clinical assessments completed, completeness of bedside documentation, number of inappropriate adjustments of resuscitation fluid rates based on urine output.

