For the qualitative aspect, study variables and themes will be assessed to include the acceptability of the intervention for healthcare workers, acceptability of the intervention for patients, burden of the intervention and protocol for healthcare workers, acceptance of the protocol, perceived knowledge gaps, comfort level with the intervention protocol, concerns with the intervention, favored aspects of the intervention. These study variables will be ascertained from the interview guides, developed using the Consolidated Frameworks for Implementation Research (CFIR).

13. Participant Timeline

Patient screening and enrollment will occur after patient assessment in the Emergency Department at Kirtipur Hospital. After consent and enrollment, randomization to the intervention bundle will occur within the ED.

Treatment will commence per intervention assignment. The patient's clinical status and specific clinical metrics will be assessed every 2 hours during the acute resuscitation period, with laboratory marker measured every 8 hours. The acute resuscitation period typically lasts 24-72 hours.

Within 2 days of completing resuscitation, each patient will undergo a 10-15 minute semi-structured interview with a research assistant regarding their experience and opinion of the resuscitation bundle.

Patients data will be followed for the duration of their inpatient hospitalization in order to track hospital course, and outcomes such as survival and disposition. All communication with the patient and their families will be in person. If the patient and their family opt to do so, they can be contacted after the conclusion of the study with notification of the study results.

14. Sample Size

We would like to update the target patient enrollment to 240 patients. The sample size calculations are demonstrated below, with a necessary sample size of 212 and a 14% increase in target enrollment to account for missing data/dropouts. We assumed an absolute difference in the prevalence of the primary outcome (24-hour UOP within target range) of 20% between the exposed and unexposed, based off of available literature. This is non-probability-based convenience sampling of patients who present with acute burn injuries to Kirtipur Hospital.

Alpha: 0.05 (95% Confidence Level)

Power: 80%

Ratio of unexposed/exposed in sample: 1

Percent of unexposed with outcome: 35%

Percent of exposed with outcome:	Prevalence Difference vs. unexposed	Odds Ratio	Necessary Sample Size

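### Section 11 requires lactate every 8 hours, but the bedside chart that feeds REDCap prints a lactate field at only 3 of its 7 laboratory time points

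*Combined protocol and SAP*

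**What the plan says.** **Schedule.** The General Resuscitation Protocol table in Section 11 lists lactate at hour 1. Its entries for hours 8 and 16 both begin "CBC, BMP, Lactate (10 mL". For the period after hour 16 it asks for "CBC, BMP, Lactate every 8 hours, and PT/PTT/INR every 24 hours until resuscitation complete". Section 13 describes follow-up "with laboratory marker measured every 8 hours" and adds: "The acute resuscitation period typically lasts 24-72 hours".

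**Record.** Section 18 has nurses and clinicians enter on the Documentation Chart "two-hourly assessments of vitals, intake, output, and symptoms and iii) 8 hourly laboratory test results". It continues: "This data will subsequently be transcribed into a secure electronic format by research assistants". The chart is therefore the source for REDCap.

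**Chart.** The laboratory results table in Appendix B has seven rows: Admission and Hours 8, 16, 24, 32, 40 and 48. CBC and BMP fields are printed in all seven. Lactate sits in a column headed "Arterial Blood Gas" and is printed only at Admission, Hour 24 and Hour 48, the same three rows that carry the coagulation fields. There is no laboratory row after Hour 48.

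**Endpoint.** Among the example variables under Primary endpoints, Section 12 lists "proportion of protocol laboratory and clinical assessments completed".

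**The concern.** A chart completed exactly as printed would not meet the Section 11 schedule. The form gives staff no lactate prompt at Hours 8, 16, 32 and 40, so a required result may not be entered and then would not reach REDCap.

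The trial sets out to measure whether a resuscitation protocol can be followed. If laboratory completion is scored against Section 11, missing lactates could come from the form and still be read as poor adherence. Section 12 also lists completeness of the bedside record. A patient's chart could be complete as printed and yet fall short on protocol laboratory assessments, and the data would not show why.

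**Working it through.** The plan states no expected completion count, so there is no figure to reproduce. The check counts printed fields against required draws.

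**Inputs**
- Required lactate times (Section 11): hours 1, 8, 16, then 24, 32, 40, 48, 56, 64, 72 while resuscitation continues. Hour 1 is matched to the chart's Admission row.
- Required coagulation times (Section 11): hour 1, then every 24 hours, taken as 24, 48 and 72.
- Length of resuscitation (Section 13): typically 24 to 72 hours.
- Printed lactate and coagulation fields (Appendix B): Admission, 24, 48. Printed CBC and BMP fields: all seven rows.

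**Lactate alone.** For resuscitation lasting T hours, required draws are T/8 + 1 if one is due at the end hour and T/8 if not.

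| Through | End-hour draw due: printed / required | End-hour draw not due: printed / required |
|---|---|---|
| 24 h | 2 / 4 | 1 / 3 |
| 48 h | 3 / 7 | 2 / 6 |
| 72 h | 3 / 10 | 3 / 9 |

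The shortfall has two parts.
- Rows that exist but print no lactate field: 2 through 24 h (hours 8, 16) and 4 through 48 h (adding 32, 40), under either reading.
- Draws with no laboratory row: 0 through 48 h. Through 72 h there are 3 (hours 56, 64, 72) or 2 (hours 56, 64), and only if no continuation sheet is used.

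**All laboratory components** (CBC, BMP, lactate, coagulation), end-hour draw due. Required = 3 × (T/8 + 1) + (T/24 + 1). Printed = 2 × rows + lactate fields + coagulation fields.
- 24 h: required 3 × 4 + 2 = 14; printed 2 × 4 + 2 + 2 = 12; 12/14 = 86%.
- 48 h: required 3 × 7 + 3 = 24; printed 2 × 7 + 3 + 3 = 20; 20/24 = 83%.
- 72 h: required 3 × 10 + 4 = 34; printed still 20; 20/34 = 59%, only if no continuation sheet is used.

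With the end-hour draw not due, the same count gives 8 of 10 through 24 h (required 3 × 3 + 1; printed 2 × 3 + 1 + 1) and 16 of 20 through 48 h (required 3 × 6 + 2; printed 2 × 6 + 2 + 2).

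**Could PDF reading have lost the cells?** CBC and BMP survive in every row, and the four rows without lactate are exactly the four without coagulation, as the 24-hour coagulation rule predicts. Random loss would not be expected to leave that pattern. The chart appears to place lactate on the 24-hour schedule, where Section 11 places it on the 8-hour one.

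**The case against.** The case for treating this as trivial has several parts.

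- **An unlabelled cell can still be used.** Staff can write a lactate value in the blank cell. This stands, so the counts describe printed prompts and are not ceilings on adherence.
- **REDCap may prompt for it.** Section 19 mentions required entries, but the REDCap form is not shown, so this is unknown either way.
- **The form in use may differ.** The chart carries a 2021 date stub, Section 18 allows further adaptation, and other parts of the chart are damaged in the extracted text. This supports checking the original page first. The match with the coagulation rows still favours a real gap.
- **Lactate alone is the harshest denominator.** This stands. Across all laboratory components the printed share is 80% or more through 48 h, and two-hourly clinical checks dilute the effect further. Even the 59% figure exceeds the 50% adherence level in Hypothesis 1. The plan does not define the counting unit: if any laboratory entry makes a time point complete, hours 8 and 16 lose nothing.

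Some stronger readings are tempting but not supported.
- A reader might infer that lactates will not be drawn. The chart table records results. Section 11 sets the draws and gives blood volumes for hours 1, 8 and 16, and nothing says that draws are ordered from the chart.
- A reader might take Sections 13 and 18 as further lactate requirements. Neither names lactate, and the 8-hourly CBC and BMP rows satisfy both through hour 48. The conflict is between Section 11 and the chart.
- A reader might treat the end of the table at Hour 48 as certain data loss. The two-hourly grid already stops at hour 24, so longer resuscitations plausibly use further sheets.

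**Conclusion.** The inconsistency is real and minor. Section 11 and the chart disagree on lactate at Hours 8, 16, 32 and 40, so required results may go unrecorded and the laboratory part of the completion measure may be understated. If only printed fields are filled, lactate completion is 2 of 4 through 24 h and 3 of 7 through 48 h. For all laboratory components it is 12 of 14 and 20 of 24. The effect on the whole measure is smaller, by an amount the documents do not allow one to calculate.

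This rests on the extracted chart matching the original page, on Admission standing for hour 1, and on staff entering only what is printed. The gap beyond Hour 48 also requires that no continuation sheet is used.

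A reader might infer bias between the arms or damage to the urine output comparison. The documents support neither: the laboratory schedule and chart serve both arms, and the urine output outcome and sample size do not depend on lactate.

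**What to change.** 1. Check the original chart page to confirm which rows print lactate.
2. Reconcile Section 11 and the chart on the lactate schedule. Which schedule is intended is for the study team to decide.
3. Make the chart labels and REDCap fields match that schedule, and confirm that a continuation sheet or further rows cover laboratory results to the end of resuscitation.
4. For patients enrolled before the change, look for lactate results in any available laboratory record. Section 19 says the chart stays in the medical record but does not mention separate laboratory reports, so some results may not be recoverable.
5. Score those patients against the Section 11 schedule in force at the time, not a later one. Report lactate completion separately from the other laboratory components so that gaps caused by the form are not read as poor adherence.

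The cost is a form revision of the kind Section 18 already allows, matching REDCap fields, and a limited record look-up. Sample size and allocation do not change.
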